2.1.3 Safety endpoints

The safety analysis will be based on the reported AEs and other safety information, such as clinical laboratory data, vital signs, ECG, physical examination (PE), weight, height, head circumference and immunogenicity.

Observation period

The observation period will be divided into the following epochs:

- The **pre-screening epoch** is defined as the time before the signed informed consent date.
- The **screening epoch** is defined as the time from the signed informed consent date up to first administration of IMP.
- The **treatment epoch for PAP** is defined as the time from the first administration of the study drug to,
 - The time just prior to the first administration of the study drug in ETP, or,
 - Four weeks (28 days) after the last infusion date if the patient does not go to ETP. If the patient enrolls in another study or receives commercially available enzyme replacement therapy (ERT), the follow-up period maybe reduced from 4 to 2 weeks.
- The **treatment epoch for ETP** is defined as the time from the first administration of the study drug in ETP to the last administration of the study drug + 4 weeks (28 days). If the patient enrolls in another study or receives commercially available ERT, the follow-up period maybe reduced from 4 to 2 weeks.
- The **post-treatment epoch for PAP** is defined as the time beyond the treatment epoch in PAP through the last study assessment; this epoch is defined only for patients who do not receive any infusion in ETP.
- The **post-treatment epoch for ETP** is defined as the time beyond the treatment epoch in ETP through the last study assessment, defined only for patients who receive any infusion in ETP.

The on-study observation period comprises of screening, treatment and post-treatment epochs. The overall alglucosidase alfa treatment period is from the first administration of alglucosidase alfa to the last administration + 4 weeks (28 days). If the patient enrolls in another study or receives commercially available ERT, the follow-up period maybe reduced from 4 to 2 weeks.

2.1.3.1 Adverse events variables

Adverse event observation period

- Pre-treatment AEs are AEs that developed or worsened or became serious during the screening epoch.
- Treatment-emergent AEs (TEAEs) are AEs that developed or worsened or became serious during the treatment epoch.
- Post-treatment AEs in PAP are AEs that developed or worsened or became serious during post-treatment epoch in PAP and could only be observed in patients who do not get an infusion in ETP.
- Post-treatment AEs in ETP are AEs that developed or worsened or became serious during the post-treatment epoch for ETP and could only be observed for patients who receive at least one infusion in ETP.

All AEs (including serious adverse events [SAE] and adverse events of special interest [AESI]) will be coded to a lower-level term (LLT), preferred term (PT), high-level term (HLT), high-level group term (HLGT), and associated primary system organ class (SOC) using the version of Medical Dictionary for Regulatory Activities (MedDRA) currently in effect at Sanofi at the time of DBL.

Serious adverse events

An SAE is any untoward medical occurrence that at any dose:

- results in death, or,
- is life-threatening, or,
Note: The term “life-threatening” in the definition of “serious” refers to an event in which the patient was at risk of death at the time of the event; it does not refer to an event which hypothetically might have caused death if it were more severe.
- requires inpatient hospitalization or prolongation of existing hospitalization, or,
- results in persistent or significant disability/incapacity, or,
- is a congenital anomaly/birth defect, or
- is a medically important event.

Medical and scientific judgment should be exercised in deciding whether expedited reporting is appropriate in other situations, such as important medical events that may not

be immediately life-threatening or result in death or hospitalization but may jeopardize the patient or may require medical or surgical intervention (i.e., specific measures or corrective treatment) to prevent one of the other outcomes listed in the definition above.

Note: The following list of medically important events is intended to serve as a guideline for determining which condition has to be considered a medically important event. The list is not intended to be exhaustive.

- Intensive treatment in an emergency room or at home for:
 - allergic bronchospasm,
 - blood dyscrasias (i.e., agranulocytosis, aplastic anemia, bone marrow aplasia, myelodysplasia, pancytopenia, etc.),
 - convulsions (seizures, epilepsy, epileptic fit, absence, etc.) ;
- Development of drug dependence or drug abuse;
- Alanine aminotransferase (ALT) $>3 \times$ upper limit of normal (ULN) + total bilirubin $>2 \times$ ULN or asymptomatic ALT increase $>10 \times$ ULN;
- Suicide attempt or any event suggestive of suicidality;
- Syncope, loss of consciousness (except if documented as a consequence of blood sampling);
- Bullous cutaneous eruptions;
- Any new invasive ventilatory support (excluding planned ventilatory support less than 3-day's duration for a planned surgical procedure).

Adverse event of special interest

An AESI is an AE (serious or non-serious) of scientific and medical concern specific to the Sponsor's product or program, for which ongoing monitoring and immediate notification by the Investigator to the Sponsor is required. Such events may require further investigation in order to characterize and understand them.

AESIs will include:

- Infusion-associated reactions (IARs):
 - IARs are defined as AEs that occur during either the infusion or the observation period following the infusion which are deemed to be related or possibly related to the IMP. At the discretion of the Investigator, AEs occurring after completion of the post-infusion observation period that are assessed as related may also be considered IARs. See more detailed definition in [Section 2.1.4](#).
- Pregnancy:
 - Pregnancy might occur in a female patient included in the clinical study. Pregnancy will be recorded as an AESI with immediate notification in all cases. It will be qualified as an SAE only if it fulfills the SAE criteria.

- Male patients will be instructed to notify the Investigator immediately if they discover that their sexual partner is pregnant.
- In the event of pregnancy in a female participant, IMP should be discontinued.
- Follow-up of the pregnancy is mandatory in a female participant or in a female partner of a male participant, until the outcome has been determined.
- Symptomatic overdose (serious or nonserious) with IMP:
 - An overdose (accidental or intentional) with the IMP is an event suspected by the Investigator or spontaneously notified by the patient and defined as at least twice the intended dose within the protocol defined therapeutic interval, adjusted according to the tested drug.

Of note, asymptomatic overdose has to be reported as a standard AE.

- Clinical laboratory (change from baseline):
 - ALT or aspartate aminotransferase (AST) increase of $\geq 3 \times$ the ULN if baseline is $< \text{ULN}$, or ALT or AST increase $\geq 2 \times$ the baseline value if baseline is $\geq \text{ULN}$;
 - A maximum ALT value of $\geq 400 \text{ IU/L}$ or AST value of $\geq 500 \text{ IU/L}$ or an increase in direct, indirect, or total bilirubin of $\geq 2 \times \text{ULN}$;
 - Serum creatinine increase of $> 1.5 \times$ the baseline value (and final serum creatinine value is $> \text{ULN}$).

2.1.3.2 Deaths

The deaths' observation periods are per the observation periods defined above.

- On-study: deaths occurring during the on-study observation period (for PAP and ETP respectively);
- Treatment: deaths occurring during the treatment epoch (for PAP and ETP respectively);
- Post-treatment: deaths occurring during the post-treatment epoch (for PAP and ETP respectively).

2.1.3.3 Laboratory safety variables

The clinical laboratory data consist of blood analysis (including hematology and biochemistry) and urinalysis. Clinical laboratory values after conversion into standard international units will be analyzed, and international units will be used in all listings and tables.

Blood samples for clinical laboratories will be taken as specified in the study protocol. The laboratory parameters will be classified as follows:

- Hematology: red blood cell count, hematocrit, hemoglobin, white blood cell count with differential count (neutrophils, eosinophils, basophils, monocytes, and lymphocytes), platelets.
- Biochemistry:
 - Plasma/serum electrolytes: sodium, potassium, chloride, calcium;

- Liver function: AST, ALT, alkaline phosphatase, gamma-glutamyl transferase, total and direct bilirubin;
- Renal function: creatinine, blood urea nitrogen, uric acid;
- Metabolic panel: glucose, albumin, total proteins, total cholesterol, triglycerides;
- Potential muscle toxicity: CK, CK with MB fraction, lactate dehydrogenase;
- Brain natriuretic peptide (BNP).
- Urinalysis will include urine color, appearance, specific gravity, proteins, glucose, erythrocytes, leukocytes, ketone bodies, and pH to be assessed:
 - Qualitatively: A dipstick is to be performed on a freshly voided specimen for qualitative detection using a reagent strip;
 - Quantitatively: A quantitative measurement for protein, erythrocytes, and leukocytes count will be required in the event that the urine sample test is positive for any of the above parameters by urine dipstick (e.g., to confirm any positive dipstick parameter by a quantitative measurement).

2.1.3.4 *Vital signs*

Vital signs include heart rate, systolic and diastolic blood pressure, respiratory rate, temperature, and oxygen saturation.

2.1.3.5 *Electrocardiogram variables*

Standard 12-lead ECGs are recorded after at least 15 minutes in the supine position using an electrocardiographic device. The following will be assessed: heart rate, rhythm, interval from start of the Q wave to the end of the S wave (QRS), interval between the peaks of successive QRS complexes (RR), interval from the beginning of the P wave until the beginning of the QRS complex (PR), interval between the start of the Q wave and the end of the T wave (QT), QT interval corrected for heart rate (QTc) automatic correction evaluation (both Fredericia and Bazett corrections by the ECG device), QRS axis, left ventricular hypertrophy criteria, right ventricular hypertrophy criteria, repolarization charges, and overall cardiac impression for each patient. For Day 1 only, and prior to receiving IMP, 3 ECGs within 5 minutes will be performed with at least 1 minute between 2 replicates.

2.1.3.6 *Physical examination*

Physical examination parameters include assessments of the patient's general appearance; skin; head, eyes, ears, nose, and throat; examinations of lymph nodes, abdomen, extremities/joints, neurological and mental status; heart and respiratory auscultation; peripheral arterial pulse; and pupil, knee, Achilles, and plantar grasp reflexes. Physical examination e-CRF also asks physician to record current muscle pain and cramps specifically at each PE assessment. Tanner stage of sexual maturation will be assessed as part of the PE assessment at baseline and yearly thereafter.

2.1.3.7 *Body weight, height/total body length, and head circumference*

Body weight will be measured in kilograms and collected monthly throughout the duration of the study. More frequent weight may be obtained at the discretion of the Investigator.

Standing height or total body length will be measured at baseline and every 3 months up to Week 73 and then every 6 months and at the end of study. If possible, height will be measured in the morning of the study visit day, prior to the PFT, and by using the same stadiometer for all measurements. Standing height is preferred, but if not possible due to patient's age or physical condition, total body length is to be measured in the same position throughout the study.

BMI will be calculated as the body weight divided by the square of the body height.

Head circumference will be measured at the same time points.

2.1.3.8 *Immunogenicity*

Immunogenicity assessments will include the following:

- During the 25-week treatment period, pre-infusion samples from patients receiving avalglucosidase alfa will be collected every month for evaluation of anti-avalglucosidase alfa ADA and every 3 months for evaluation of anti-alglucosidase alfa ADA. In addition, samples will be collected at Visit 3 (Day 8) to monitor for an early antibody response using both assays. For patients receiving alglucosidase alfa, only anti-alglucosidase alfa ADA will be evaluated.
- During the 120-week extension period, pre-infusion samples from all patients will be collected every 3 months for evaluation of anti-avalglucosidase alfa ADA and every 6 months for evaluation of anti-alglucosidase alfa ADA. In addition, participants in Cohort 3 switching to avalglucosidase alfa will have samples collected at Visit 17 (Week 28) to monitor for an early antibody response using both assays, followed by collection every month for 6 months and then every 3 months for evaluation of anti-avalglucosidase alfa ADA.
- ADA seropositive patient serum will be assessed for neutralizing antibodies (NAbs) to avalglucosidase alfa and/or alglucosidase alfa, as appropriate, including inhibition of enzyme activity and uptake.

Samples may be collected from patients and evaluated for anti-drug IgE, complement activation, serum tryptase following moderate, severe, or recurrent mild IARs suggestive of hypersensitivity reactions.

In the event a patient exhibits signs or symptoms suggestive of systemic immune complex mediated reactions involving skin and other organs, serum samples are obtained for the evaluation of circulating immune complexes.

The qualitative sample status of the ADA will be assessed and be categorized into the following classes:

- ADA-negative sample: a sample is considered negative if ADAs are not detected (i.e., negative in screening assay or reactive in screening but negative in confirmatory assay).
- ADA-positive sample: sample in which ADA is detected (i.e., sample generates an assay signal equal to or greater than the cut-point in the screening assay and is tested positive in the confirmatory assay).

The ADA titer of the positive samples will also be assessed. A titer represents quasi-quantitative information on the level of ADA present in a sample. Confirmed positive samples are serially diluted until a negative result is achieved. The titer is subsequently defined as the reciprocal of the last dilution that tests positive. The minimal required dilution (MRD) will be incorporated in the final calculation.

The ADA attributes will be determined by the following conditions:

- Pre-existing ADAs: antibodies reactive with the study drug present in patient at the baseline assessment.
- Treatment induced ADAs: ADAs developed de novo (seroconversion) following administration of the study drug. If the baseline ADA sample is missing or non-reportable and at least one reportable on-treatment ADA sample is available, the baseline sample will be considered as “negative”.
- Treatment boosted ADAs: Pre-existing ADAs that were boosted at least two titer steps from baseline (i.e., 4 fold increase in titers) following administration of the study drug (any time after the first drug administration).

The following kinetics of the ADAs will be analyzed:

- Onset of ADA is defined as the time period (in days) between the first study drug administration and the first instance of treatment induced ADAs.
- Duration of ADA will be calculated as the date of last treatment induced ADA sample minus the date of first treatment induced or boosted ADA sample + 1.
- Persistent ADA response is defined as,
 - Treatment induced ADAs detected at two or more sample time points during the treatment, where the first and last ADA-positive on-treatment sample (irrespective of any negative samples in between) are separated by at least 16 weeks.

- Transient ADA response is defined as,
 - Treatment induced ADA detected only at one sampling time point during the treatment, followed by an ADA-negative value; Or,
 - Treatment induced ADA detected at two or more sampling time points during the treatment, where the first and last ADA-positive samples are separated by a period less than 16 weeks, and the patient's last sample time point is ADA-negative.
- Indeterminate ADA response is defined as,
 - Only the last sample time point is positive; Or
 - The last sample time point is positive and separated by <16 weeks from the first positive result.

Treatment-boosted ADAs are excluded from the analysis of ADA kinetics. If many patients have preexisting ADAs, kinetics of boosting will be described separately.

For the assessment of NAb response, the qualitative sample status will be assessed and be categorized into the following classes:

- NAb-negative sample: a sample is considered negative if NAb are not detected.
- NAb-positive sample: sample in which NAb is detected.

2.1.4 Infusion associated reactions

Protocol-defined IARs

IARs are defined as AESIs that occur during either the infusion or the observation period following the infusion which are deemed to be related or possibly related to the IMP. At the discretion of the Investigator, AEs occurring after completion of the post-infusion observation period that are assessed as related or possibly related may also be considered IARs. AESIs defined in protocol only include the protocol-defined IARs.

Algorithm-defined IARs

An alternative definition of IAR is defined as any treatment-emergent AE meeting one of the following criteria:

- Event occurs from the start of infusion to the end of infusion plus 24 hours window, and considered related study drug;
- If AE start date is non-missing but time component is missing, compare AE Start date with infusion start date (date component only) and infusion end date (date component only). If AE Start date is between infusion start date and infusion end date plus one day, consider such AE as algorithm-defined IAR if AE is related to study drug.

The algorithm-defined IAR will be summarized as supplementary to the protocol-defined IARs for the safety review.

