8.3 BLINDING PROCEDURES

8.3.1 Methods of blinding

This study is an open-label design.

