10.4.2 General guidelines for reporting adverse events

- All AEs, regardless of seriousness or relationship to IMP/NIMP, spanning from the signature of the ICF until the end of the study as defined by the protocol for that patient, are to be recorded on the e-CRF.
- Whenever possible, diagnosis or single syndrome should be reported instead of symptoms. The Investigator should specify the date of onset, intensity, action taken with respect to study treatment, corrective treatment/therapy given, additional investigations performed, outcome, and his/her opinion as to whether there is a reasonable possibility that the AE was caused by the study treatment or by the study procedure(s).
- If the Investigator assesses the AE related to study treatment and the Investigator cannot reasonably explain the AE by other factors (such as clinical state, concomitant therapy, and /or other interventions) or if the cause of the AE is unknown by the Investigator, the relationship to study treatment must be checked "Related" by the Investigator.
- The Investigator should check "Not Related" when there is a clear alternative cause to the event other than the study treatment according to the Investigator.

There is one exception to this rule. In instances where a patient experiences an IAR (refer to [Section 10.6](#)), allergic, or anaphylactic reaction, either during infusion or post observation period, each of the individual signs and/or symptoms comprising the reaction should be captured as individual AE terms.

- The Investigator should take appropriate measures to follow all AEs until clinical recovery is complete and laboratory results have returned to normal, or until progression has been stabilized, or until death, in order to ensure the safety of the patients. This may imply that observations will continue beyond the last planned visit per protocol, and that additional investigations may be requested by the monitoring team up to as noticed by the Sponsor.
- When treatment is prematurely discontinued, the patient's observations will continue until the end of the study as defined by the protocol for that patient.
- Laboratory, vital signs or ECG abnormalities are to be recorded as AEs only if:
 - Symptomatic, and/or
 - Requiring either corrective treatment or consultation, and/or
 - Leading to IMP discontinuation or modification of dosing, and/or
 - Fulfilling a seriousness criterion, and/or
 - Defined as an AESI.

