- All TEAEs during PAP presented by PT, sorted by decreasing incidence of PT in the avalglucosidase alfa arm.

- All TEAEs regardless of relationship and related to IMP during PAP by primary SOC, and PT.
- All TEAEs during PAP by maximal severity (i.e., mild, moderate, or severe), presented by primary SOC and PT.
- Most common TEAEs during PAP by primary SOC and PT sorted by the internationally agreed SOC order and by decreasing incidence of PTs within each SOC. The most common TEAE are defined as those preferred terms occurring in ≥ 2 patients.
- Listing of TEAEs.

Analysis of treatment-emergent SAE(s) in PAP

- All treatment-emergent SAEs during PAP, by primary SOC and PT.
- All treatment-emergent SAEs regardless of relationship and related to IMP during PAP, by primary SOC and PT.
- Listing of treatment-emergent SAEs.

Analysis of TEAE(s) leading to treatment discontinuation in PAP

- TEAEs leading to permanent treatment discontinuation during PAP, by primary SOC and PT.
- TEAEs leading to permanent treatment discontinuation during PAP presented by PT, sorted by decreasing incidence of PT in the avalglucosidase alfa arm.
- Listing of TEAEs leading to permanent treatment discontinuation during PAP, including details on dose, severity, and relationship, etc.

Analysis of adverse events with AESIs in PAP

- Treatment-emergent AESIs during PAP, by primary SOC and PT, showing the n and % of patients, sorted by decreasing incidence of PT within the avalglucosidase alfa arm.
- Treatment-emergent protocol-defined IARs during PAP, by primary SOC and PT, presented by overall n and %, as well as by start time of IAR in relation to end of infusion time (during infusion, ≤ 2 hours, >2 to 24 hours, >24 to 72 hours, >72 hours).
- Treatment-emergent algorithm-defined IARs during PAP, by primary SOC and PT, presented by overall n and %, as well as by start time of IAR in relation to end of infusion time (during infusion, ≤ 2 hours, >2 to 24 hours, >24 to 72 hours, >72 hours).
- Treatment-emergent protocol-defined IARs during PAP, by PT and maximal severity, presented by overall n and %, as well as by start time of IAR in relation to end of infusion time (during infusion, ≤ 2 hours, >2 to 24 hours, >24 to 72 hours, >72 hours).

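### Both IAR definitions rest on the open-label investigator's relatedness call, so the supplementary one cannot show whether a Cohort 3 difference in IARs reflects labelling

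*SAP*

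**What the plan says.** SAP 2.1.4 defines an IAR in two ways.

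- **Protocol-defined:** AEs during the infusion or the observation period after it "which are deemed to be related or possibly related to the IMP". Later related events may be added at the investigator's discretion.
- **Algorithm-defined, time known:** "Event occurs from the start of infusion to the end of infusion plus 24 hours window, and considered related study drug".
- **Algorithm-defined, time missing:** the AE date is compared with the infusion dates (end date plus one day), and then "consider such AE as algorithm-defined IAR if AE is related to study drug".

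On the role of the second definition, the SAP states: "The algorithm-defined IAR will be summarized as supplementary to the protocol-defined IARs for the safety review".

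Protocol 10.4.2 makes causality the investigator's call, namely "his/her opinion as to whether there is a reasonable possibility that the AE was caused by the study treatment". An event is marked not related "when there is a clear alternative cause to the event other than the study treatment", and an event of unknown cause has to be marked related. Protocol 8.3.1 states: "This study is an open-label design".

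SAP 2.4.4.1 tabulates both versions for the primary analysis period (PAP), for example "Treatment-emergent algorithm-defined IARs during PAP, by primary SOC and PT", with a breakdown by onset relative to the end of infusion. AE summaries in that section are by study cohort and treatment group, so the two Cohort 3 arms stand side by side.

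**The concern.** A supplementary definition adds information to the extent that it depends on something the main one does not. Here the window differs but the subjective input is shared.

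The two Cohort 3 arms also differ in how familiar the drug is to the person making the call. Controls continue an enzyme they have had at a stable dose for at least 6 months (Protocol 7.1, I 05), and children at high risk of a severe allergic reaction, judged largely from past reactions or antibodies to that enzyme, are excluded (Protocol 7.2.1, E 05). The other arm starts a drug whose first use in infantile-onset disease is this study (Protocol 4). An investigator who knows the arm could judge the same event differently.

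Safety is the primary endpoint, IARs are named in it, and Cohort 3 is the only randomised part of the study. If labelling differed by arm, both IAR tables would carry the difference, and their agreement would look like corroboration without being so. The same label feeds the IAR summaries by antibody category (SAP 2.4.6).

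**Working it through.** **1. Is any planned table both tied to the infusion and free of the causality call?** The documents state no IAR rate or sample-size figure to reproduce, so the first check is of the text.

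| Planned PAP output (SAP 2.4.4.1) | Tied to infusion time | Free of relatedness |
|---|---|---|
| Protocol-defined IARs, with onset split | yes | no |
| Algorithm-defined IARs, with onset split | yes | no |
| All TEAEs, regardless of relationship and related | no | yes (all-cause part) |
| Hypersensitivity/anaphylaxis query search | no | yes |

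No row has yes in both columns. Every onset-time split is of events already selected as related.

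**2. What could a labelling difference do?** All inputs here are assumptions except the arm size, about 5 per arm from at least 10 patients randomised 1:1.

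- One child counts for 1/5 = 20 percentage points.
- Let in-window AEs per child be Poisson with mean L, the same in both arms, and let each be called related with probability r. Then P(child has an IAR) = 1 − exp(−L·r).
- The chance that avalglucosidase alfa shows at least 2 more children with an IAR is the sum of Bin(i; 5, p₁)·Bin(j; 5, p₂) over i − j ≥ 2.

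With L = 1, 1 − exp(−1) = 63% of children in each arm have an in-window AE:

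| r, new drug / control | IAR %, new drug / control | Chance of excess ≥ 2 children on new drug |
|---|---|---|
| 0.5 / 0.5 | 39 / 39 | 17% |
| 0.7 / 0.3 | 1 − e^(−0.7) = 50 / 1 − e^(−0.3) = 26 | 44% |
| 0.8 / 0.2 | 1 − e^(−0.8) = 55 / 1 − e^(−0.2) = 18 | 61% |
| relatedness not required | 63 / 63 | 16% |

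Over L = 0.5 to 3, the chance is 12% to 17% with 0.5/0.5, 28% to 52% with 0.7/0.3, and 39% to 74% with 0.8/0.2. Without the relatedness condition it is 2% to 17%. Swapping the r values between arms gives the same gaps in the other direction.

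**3. Would an all-cause count by itself be fair between arms?** Not if it is given only as a percentage of patients. Every-other-week dosing gives 13 infusions by Week 25 (Protocol 8.1.1). Weekly control dosing (Protocol 10.1.2.3) gives one in each of Weeks 1 to 25, so 25.

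Take an assumed background of 60% of children with an in-window AE over 13 windows:

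- Rate per window: −ln(0.4)/13 = 0.0705.
- Weekly child over 25 windows: 1 − 0.4^(25/13) = 83%, which is 23 points higher with no drug effect.
- Rate per infusion: 0.0705 on either schedule.

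The added count therefore needs a per-infusion denominator.

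**The case against.** The strongest reply is that the plan already gives the means to notice differential labelling. All-cause and related TEAEs are tabulated by arm, so a difference in the related share could be seen. A programmed query search for hypersensitivity and anaphylaxis, with by-patient listing and medical review, does not use the causality field. AE listings show relationship for each patient, and in a cohort of about 10 they can be read child by child. An allergist/immunologist reviews IARs (Protocol 6.4.1). Unknown cause must be marked related, and SAP 2.5.2 counts a missing relationship as possibly related.

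This stands as partial mitigation. A reader might infer that a spurious or hidden IAR difference could never be recognised; the documents do not support that. What they lack is a display of peri-infusion events free of the causality call. The two default rules narrow discretion without removing it, and no rule lets the allergist's review change the relatedness used in the tables.

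Two further replies also hold. Relatedness is part of what this trial means by an IAR, and the SAP presents the algorithm only as supplementary, so dropping the condition from the definition would put peri-infusion AEs under an IAR heading. And safety is as-treated and descriptive with no inferential test (SAP 2.4.4), so no error rate or decision rule is affected.

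**Conclusion.** The point holds as one of interpretation. Both IAR definitions share one open-label judgement, so the second varies the window and cannot test the labelling.

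A reader might go further and infer that IARs on avalglucosidase alfa will be inflated. The documents support only that the counts *can* differ through labelling. They give no related rates and no direction. That a familiar drug makes another cause easier to name is plausible but unsourced, and Protocol 8.8.1 notes that infusion reactions occurred in trials of both enzymes.

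The 24-point gap (50% against 26%) rests on assumed values of L and r and on equal true risk. The firm figure is 20 points per child at 5 per arm. With so little data and no test, the harm is a table that may be misread. The remedy uses data already collected, so it is worth making.

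**What to change.** In SAP 2.1.4 and 2.4.4.1:

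- Leave both IAR definitions unchanged.
- Add a supplementary PAP row, by cohort and treatment arm, of all TEAEs with onset from infusion start to 24 hours after infusion end, regardless of relationship. Use the existing date rule when the time is missing.
- Show the related subset beside it, so the related share can be read for each arm.
- Give n and % of patients, and also events per infusion or the percentage of infusions with an event.

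The cost is one row and one denominator per table, with no new data and no change to patient care. The downside is that background events enter the count. The row also does not equalise observation. During the PAP, home infusion is open only to controls (Protocol 8.9.1, 8.9.2), and on-site stays of at least 8 hours for PK sampling apply only to avalglucosidase alfa patients (Protocol 10.1.2.1, 10.1.2.6). A table note should say so.
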